### 5.4. Primary endpoints

- Changes in indicators of nutritional habits (preference towards healthy foods, perceived benefits of healthy eating, fast food intake, family meal frequency, having breakfast on a regular basis; attitudes regarding eating) among these adolescents at 3 and 6 months.
- Changes in food insecurity in households (based on the Food Insecurity Questionnaire) at 3 and 6 months;

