### 6. Project design

We will perform an interventional study on food security, psychological wellbeing and healthy eating using a sample of Portuguese adolescents. An e-platform, an app and specific psycho-educative sessions will be developed to support this study.

About 300 community adolescents from two schools will be invited to participate in a study. The intervention length is 6 months: (i) three months of direct intervention; (ii) evaluation at baseline, month 3, and follow-up at month 6.

- (i) Evaluation at baseline (T0)
- Application of validated questionnaires;
- Collection of anthropometric measures;
- Introduction to the use of the platform and the app;
- One psycho-educative session on healthy life styles for adolescents and another for parents.
- (ii) Evaluation at 3-months (T1)
- Application of validated questionnaires;
- Collection of anthropometric measures;
- One psycho-educative session for adolescents and another for parents. The psycho-educative sessions will focus on the discussion of the strategies to improve health lifestyles which have meanwhile been developed in the platform and the app some of them by the adolescents themselves.
- (iii) Evaluation at 6-months (T2)
- Application of validated questionnaires; collection of anthropometric measures.

The interactive e-platform and app will allow for the delivery and collection of information; discussion of nutritional and physical activities; share of solutions and strategies; favor cohesion among adolescents; promotion of behavior change. Psycho-

educative sessions will play an important role for discussing potential strategies to promote change.

The same validated questionnaires will be applied at T0, T1 and T2. Our team will apply robust statistical methods. The trial will follow the principles of best clinical practices, all adolescents and their parents will sign an informed consent and all procedures will be submitted to an Ethics Committee and to *Ministério da Educação* – *Monitorização dos inquéritos em meio escolar*.

Our aim is to assess the short and long-term change in clinical endpoints. This study has a high likelihood of success attending to the vast expertise of the team members involved in handling large studies, psychosocial variables assessment, interventions with adolescents, development of psycho-educative sessions, and management of group dynamics.

To accomplish our aims, this project comprises the following tasks:

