### 11.2. Statistical methods

Quantitative analysis will be performed with SPSS and AMOS. In the quantitative analysis, continuous variables will be reported as mean and standard deviation. Qualitative analysis will be performed with NVivo program.

In Study 1, we will perform clusters analysis in order to identify adolescents with food insecurity. In Study 2, we will perform structural equations modeling in order to analyze whether well-being is a mediator variable between food insecurity and disordered eating, and whether sex is a moderator variable. Multilevel analysis will be performed in Study 3. In Study 4, in order to analyze the qualitative data we will conduct Thematic Analysis (NVIVO program). Finally, in Study 5, we will conduct repeated-measures factorial ANOVASs for each variable; the analyses will be complemented with multiple comparisons using Bonferroni adjustment at p < .05.

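### Seven unranked primary indicators are analysed one by one with no written adjustment across them; if any one counts as success, familywise error is about 30% under independence

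*Protocol*

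**What the plan says.** Protocol section 5.4 has two primary-endpoint bullets, both assessed at months 3 and 6. The first covers nutritional habits and spells out six indicators: "preference towards healthy foods, perceived benefits of healthy eating, fast food intake, family meal frequency, having breakfast on a regular basis; attitudes regarding eating". The second is "Changes in food insecurity in households (based on the Food Insecurity Questionnaire) at 3 and 6 months". The section ranks none of the seven, defines no composite score, and does not say how many must improve.

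The impact analysis is Study 5. For it, section 11.2 plans "repeated-measures factorial ANOVASs for each variable; the analyses will be complemented with multiple comparisons using Bonferroni adjustment at p < .05". The 5% level appears once, beside the Bonferroni comparisons. No level is given for the overall F tests, and the factors of the factorial ANOVA are not named.

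Section 6 fixes three measurement occasions: "The same validated questionnaires will be applied at T0, T1 and T2". Section 8.4 describes the Study 5 outcomes by an open list of examples. Of the seven primary indicators, that list names only eating attitudes.

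**The concern.** The protocol does choose a multiplicity procedure, and a reader who sees the word Bonferroni may take the matter as settled. But the procedure is attached to the comparisons that follow each ANOVA. With three visits, these are the three visit pairs within a variable, plus any factor-level contrasts. It answers which visits differ for a given indicator. It does not address the larger question: how often at least one of seven primary indicators would look changed if none had.

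Section 5.1 sets the aim of testing effectiveness. With seven primary indicators of equal standing and no rule for combining them, whichever reaches significance can be reported as meeting a primary endpoint. A positive primary statement then carries less weight than its nominal 5% suggests.

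**Working it through.** The protocol states no familywise error rate and no power calculation (section 11.1 gives only 300 adolescents), so there is no figure of its own to reproduce.

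**Inputs from the protocol**
- Primary indicators: 6 + 1 = 7 (section 5.4).
- One repeated-measures ANOVA per variable (section 11.2).
- Three visits, so 3 visit pairs per variable (section 6).

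**Assumptions, not stated in the protocol**
- Each overall test uses 5%.
- Any one significant indicator counts as primary success.
- The correlation between indicators is unknown, so a range is shown.

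**Step 1. Independence.** The chance of at least one false positive in seven tests is 1 − (1 − 0.05)^7 = 1 − 0.95^7 = 1 − 0.6983 = 0.302, or about 30%.

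**Step 2. Upper bound.** Under any dependence, the chance cannot exceed the sum of the levels: 7 × 0.05 = 0.35.

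**Step 3. Correlated indicators.** The overall time effect over three visits has 2 degrees of freedom. In large samples its 5% critical value is −2 ln(0.05) = 5.99. Seven such statistics with equal pairwise correlation ρ were simulated under no change (200,000 replicates). The third column judges success on the within-variable Bonferroni visit comparisons instead, each at 0.05/3.

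| Assumed ρ | At least one of 7 overall tests | At least one of 7 by visit pairs at 0.05/3 |
|---|---|---|
| 0 | 30.1% | 27.1% |
| 0.2 | 28.7% | not run |
| 0.3 | 27.4% | 24.8% |
| 0.5 | 23.4% | 21.2% |
| 0.7 | 18.5% | not run |
| 0.8 | 15.3% | 14.0% |
| 0.9 | 11.7% | not run |

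The third column shows that the planned Bonferroni step does its own job: the error for a single variable is 4.4%. It barely changes the error across the seven.

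**Step 4. Other readings of the text**
- If each bullet were one composite endpoint, there would be two tests: 1 − 0.95^2 = 9.75% under independence.
- If Bonferroni were meant to cover all 7 × 3 = 21 visit comparisons, the simulated familywise error of those comparisons is 4.7% at ρ = 0. The overall F tests would still be unadjusted.

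**Step 5. With adjustment across the seven.** When nothing changes, Holm's first step decides, at 0.05/7 = 0.00714. The familywise error is then 1 − (1 − 0.00714)^7 = 4.9% under independence. In simulation it is 4.7% at ρ = 0.3 and 4.1% at ρ = 0.5. It is at most 5% under any dependence.

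**The case against.** The strongest reply is that the 30% rests on conditions the protocol does not state. Section 11.2 gives no level for the overall tests and does not say that Bonferroni stops at the single variable. No success rule makes one indicator sufficient. All seven come from the same adolescents and households and most concern related eating behaviour, so independence is unlikely. The count of seven comes from unpacking a parenthesis in section 5.4, and the open list in section 8.4 does not fix which ANOVAs serve the primary endpoints. All of this stands as a limit on the figure. A reader might infer that the trial has a 30% false-positive rate as a matter of fact; the document does not support that.

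The adjustment itself does not depend on those points. No composite is described, and section 11.2 analyses each variable separately. The Bonferroni step is attached to the comparisons that complement each ANOVA. Even a correlation of 0.9 leaves 11.7%, and two composites leave 9.75%.

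A second reply is that such detail belongs in a statistical analysis plan, which may exist and is not shown. That would answer a complaint about mere silence. Here the protocol itself fixes several unranked primary endpoints and chooses a multiplicity step that, as naturally read, does not reach across them.

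A reader might also add the section 5.5 variables to enlarge the figure. Those are secondary, so the total would not be a primary error rate. Clustering within classes is a separate matter and plays no part in this point.

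**Conclusion.** The point holds in conditional form. That no adjustment across the seven primary indicators is written, and that none is ranked, can be read from sections 5.4 and 11.2 with high confidence. The size is less certain. Given 5% per overall test and success on any one indicator, familywise error is about 30% under independence and never above 35%. It is roughly 23% to 27% at assumed correlations of 0.5 to 0.3. These correlations are assumptions; the protocol gives no basis for choosing among them. The unnamed factors could add further F tests per variable and raise the figure.

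This should be corrected, because it affects what a primary success would mean. It does not invalidate the data collection.

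**What to change.** In section 11.2, name the overall time effect as the primary test for each of the seven variables in section 5.4, and apply Holm across those seven tests at a familywise 5%. The smallest p-value is compared with 0.05/7 = 0.0071, the next with 0.05/6 = 0.0083, and so on up to 0.05, stopping at the first failure. Keep Bonferroni for the T0, T1 and T2 comparisons within a variable, where it shows which visits differ. State that the section 5.5 variables are secondary and lie outside this family.

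The cost is a change of wording and a stricter threshold for each primary indicator, hence some loss of power. No new data are needed, and the stated objectives and the 3- and 6-month assessments stay as they are.

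An alternative is to name household food insecurity as the single primary endpoint, tested at 5%. It is the subject of hypothesis (i) in section 4 and of the second primary objective in section 5.2. But the eating-habits part of the first primary objective would then have no primary endpoint, so section 5.2 would also need rewording. Narrowing further to one visit would depart from the two time points in section 5.4. That is a choice for the sponsor; the Holm route avoids it.

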### 12. Ethical conduct

### 12.1. Independent Ethics Committee or Institutional Review Board

Prior to initiation of the project at any site, the project, including the protocol, informed consent, and other project documents must be approved by an appropriate IRB/IEC. The IRB/IEC must be constituted according to applicable regulatory requirements.

In the event that the IRB/IEC requires changes in the protocol, the sponsor shall be advised and must approve the changes prior to implementation. The investigator shall not modify the project described in the protocol once finalized and after approval by the IRB/IEC without the prior written approval of sponsor.

### 12.2. Subject information and consent

The details of the protocol must be provided in written format and discussed with both parents and adolescents. Parental written informed consent must be obtained as well as adolescent's written assent before any project-related procedure is performed. In obtaining informed consent, the information must be provided in language and terms understandable to the subject. The subject, or the subject's legal representative, must give their written consent to participate in the interventional study. The signed and dated consent form itself must be retained by the investigator as part of the project records. A copy of the signed and dated consent form must be given to the subject. The consent form must include all of the required elements of informed consent in accordance with ICH Guidelines E6 and local laws.

The consent form must be approved by the appropriate IRB/IEC and sponsor before trial initiation at a project site. Any subsequent changes to the approved informed

consent form must be reviewed and approved by the appropriate IRB/IEC and sponsor before implementation.

### 12.3 Protection and confidentiality of participants' data

The confidentiality of participants' data will be ensured. Identification numbers will be used for logistic reasons, although they will be saved independent of other data. These data will be not divulgated by other institutions without involvement in the project.

All the participants' data will be encrypt to preserve the anonymity of each individual, according to the obligations described in the Law dispatch 20510/2008, of July 24th. In the transference of the clinical data to a database from the SPR, the data encryption process will enable the guarantee of the confidentiality and anonymity of each individual. It will be available a code number to decode the subjects' identity. This code number will be just available for the principal investigator, in a different place of the other data. The computer where the data will be centralized will be available in the SPR, with restrict access (with an username and password) for the principal investigator, or other person designated for that propose.

### 13. Participants' insurance

Not applicable.

### 14. Publications and other rights

### 14.1 Rights to publish by investigator

The investigator has the right to publish or publicly present the results of the project in accordance with this Section 12.1 of the protocol.

The investigator agrees not to publish or publicly present any interim results of the project without the prior written consent of the sponsor. The investigator further agrees to provide to the sponsor 45 days prior to submission for publication or presentation, review copies of abstracts or manuscripts for publication (including, without limitation, slides and texts of oral or other public presentations and texts of any transmission through any electronic media, e.g., any computer access system such as the Internet, World Wide Web, etc) that report any results of the project. The sponsor shall have the right to review and comment with respect to publications, abstracts, slides, and manuscripts and the right to review and comment on the data analysis and presentation. If the parties disagree concerning the appropriateness of the data analysis and presentation, and/or confidentiality of the sponsor's confidential information, investigator agrees to meet with the sponsor's representatives at the project site or as otherwise agreed, prior to submission for publication, for the purpose of making good faith efforts to discuss and resolve any such issues or disagreement.

### 14.2 Use of proprietary or confidential information in a Publication

No publication or manuscript shall contain any trade secret information of the sponsor or any proprietary or confidential information of the sponsor and shall be confined to new discoveries and interpretations of scientific fact. If the sponsor believes there is patentable subject matter contained in any publication or manuscript submitted

for review, the sponsor shall promptly identify such subject matter to investigator. If sponsor requests and at sponsor's expense, investigator shall use its best efforts to assist sponsor to file a patent application covering such subject matter with the USA Patent and Trademark Office or through the Patent Cooperation Treaty prior to any publication.

### 14.3 Use of project information in a publication

Investigator is granted the right subject to the provisions of this protocol to use the results of all work provided by investigator under this protocol, including but not limited to, the results of tests and any raw data and statistical data generated for investigator's own teaching, research, and publication purposes only. Investigator/Institution agrees, on behalf of itself and its employees, officers, trustees, and agents, not to cause said results to be knowingly used for any commercial purpose whatsoever except as authorized by the sponsor in writing.

### 14.4 Authorships of publications

Authors of publications must meet the International Committee of Medical Journal Editors (ICMJE) guidelines for authorship and must satisfy the 3 criteria that follow:

- a) Authors must make substantial contributions to the conception and design of the project, acquisition of data, or analysis of data and interpretation of results;
- b) Authors must draft the publication or, during draft review, provide contributions (data analysis, interpretation, or other important intellectual content) leading to significant revision of the manuscript with agreement by the other authors;

c) Authors must provide written approval of the final draft version of the publication prior to submission.

All contributors who do not meet the 3 criteria for authorship should be listed in an acknowledgments section within the publication, if allowed by the journal, per the ICMJE guidelines for acknowledgment.

### 15.2 Investigators

### **15.2.1 Selecting Investigators**

Only investigators qualified who have the knowledge, skills and experience to successfully achieve the project's goals are selected.

